8.2.4 Key Secondary Endpoints

The key secondary endpoints are:

- Change from baseline in itch-related quality of life at the end of Week 12 of the Double-blind Treatment Period, as assessed by the 5-D Itch Scale;
- Change from baseline in itch-related quality of life at the end of Week 12 of the Double-blind Treatment Period, as assessed by the total Skindex-10 Scale score;
- Proportion of subjects achieving ≥ 4 -point improvement from baseline with respect to the weekly mean of the daily 24-hour Worst Itching Intensity NRS at Week 12 of the Double-blind Treatment Period;

8.2.4.1 5-D Itch Scale

The 5-D Itch Scale was developed as a brief but multidimensional questionnaire designed to be useful as an outcome measure in clinical trials. The 5 dimensions of itch being assessed are degree, duration, direction, disability, and distribution (see protocol Appendix 4).

The duration, degree, and direction domains each include 1 item, while the disability domain has 4 items. All items of the first 4 domains were measured on a 5-point Likert scale. The distribution domain included 16 potential locations of itch, including 15 body part items and 1 point of contact with clothing or bandages.

Single-item domain scores (duration, degree, and direction) are equal to the value indicated below the response choice (range 1–5). The disability domain includes 4 items that assess the impact of itching on daily activities: sleep, leisure/social activities, housework/errands, and work/school. The score for the disability domain is achieved by taking the highest score on any of the 4 items. For the distribution domain, the number of affected body parts is tallied (potential sum 0–16), and the sum is sorted into 5 scoring bins: sum of 0–2 = score of 1, sum of 3–5 = score of 2, sum of 6–10 = score of 3, sum of 11–13 = score of 4, and sum of 14–16 = score of 5.

The scores of each of the 5 domains are achieved separately and then summed together to obtain a total 5-D score. 5-D scores can potentially range between 5 (no pruritus) and 25 (most severe pruritus).

Total 5-D Itch score = duration score (single item) + degree score (single item) + duration score (single item) + maximum (4 disability items) + category score based on sum of affected body parts.

The scoring manual does not give specific direction regarding scoring when some questions are missing; therefore, each domain and the total score will be set to missing when any of their individual components are missing, with the exception of the disability domain. The maximum of any items is present for disability will be used for that domain. Missing data will be handled implicitly in the MMRM model or explicitly via multiple imputation (see below).

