14.4 Appendix 4: 5-D Itch Scale

This is a representation of the content of the instrument to be used. Please refer to the Study Reference Manual for the instrument to be administered to patients and instructions.

1. DURATION:	During the last 2 weeks, how many hours a day have you been itching?						
	Less than 6 hrs/day	6-12 hrs/day	12-18 hrs/day	18-23 hrs/day	All day		
							
2. DEGREE:	Please rate the intensity of your itching over the past 2 weeks						
	Not present	Mild	Moderate	Severe	Unbearable		
							
3. DIRECTION:	Over the past 2 weeks has your itching gotten better or worse compared to the previous month?						
	Completely resolved	Much better, but still present	Little bit better, but still present	Unchanged	Getting Worse		
							
4. DISABILITY:	Rate the impact of your itching on the following activities over the last 2 weeks						
	Sleep	Never affects sleep	Occasionally delays falling asleep	Frequently delays falling asleep	Delays falling asleep and occasionally wakes me up at night	Delays falling asleep and frequently wakes me up at night	
							
		N/A	Never affects this activity	Rarely affects this activity	Occasionally affects this activity	Frequently affects this activity	Always affects this activity
	Leisure/Social						
	Housework/Errands						
	Work/School						

5. DISTRIBUTION:	Mark whether itching has been present in the following parts of your body over the last 2 weeks. If a body part is not listed, choose the one that is closest anatomically.			

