1. PURPOSE OF THE ANALYSES

This is a multicenter, randomized, double-blind, placebo-controlled study to evaluate the safety and efficacy of intravenous (IV) CR845 for the treatment of chronic kidney disease-associated pruritus (CKD-aP) in hemodialysis patients at a dose of 0.5 mcg/kg administered after each dialysis session compared to placebo. The study includes a double-blind phase and an open-label extension phase.

This statistical analysis plan (SAP) provides a detailed description of the strategy and statistical methodology to be used for analysis of data from the double-blind phase of the CR845-CLIN3102 protocol. The open-label analyses will be addressed in a separate document.

The purpose of the SAP is to describe the pre-specified statistical approaches to the analysis of study data prior to database lock. This analysis plan is meant to supplement the study protocol. If differences occur between analyses described in the SAP and the current protocol, those found in this SAP will assume primacy. Any deviations from this plan will be described in the Clinical Study Report.

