8.1.3 Multiplicity Handling

The efficacy of CR845 0.5 mcg/kg compared to placebo in pivotal phase 3 study CLIN3102 will be evaluated based on 1 primary and 3 secondary efficacy endpoints.

Testing of the primary efficacy endpoint will be 2-sided and conducted at the 5% error level. The study will be considered positive if the null hypothesis of no treatment difference in the primary efficacy analysis of the primary endpoint (proportion of subjects achieving ≥ 3 -point improvement from baseline with respect to the Worst Itching Intensity NRS at Week 12 of the Double-blind Treatment Period) is rejected in favor of the alternative that subjects randomized to CR845 experience significantly less itching compared to subjects randomized to placebo.

To protect the Type 1 error, a gate-keeping strategy will be implemented. Although the p-values corresponding to the hypothesis testing of the secondary variables will be reported, they will only be considered inferential if the primary analysis is statistically significant. Testing of the 3 secondary efficacy endpoints will be performed sequentially at a 2-sided 5% error level. The difference between CR845 0.5 mcg/kg and placebo with respect to the 5-D Itch total score will be tested first using the ANCOVA approach in section [8.2.4.3](#). If results are statistically significant in favor of CR845, testing with respect to the Skindex-10 total score will be conducted, also using ANCOVA. The proportion of subjects achieving ≥ 4 -point improvement from baseline with respect to the weekly mean of the daily 24-hour Worst Itching Intensity NRS at Week 12 of the

Double-blind Treatment Period will be tested only if the results of Skindex-10 total score are statistically significant in favor of CR845.

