- For each questionnaire, the total score at each visit will be computed from the domain scores for each imputed dataset.
- The ANCOVA analysis described above will be implemented for each imputed dataset.
- Results of the ANCOVA on the multiply imputed data sets will be summarized by the SAS MIANALYZE procedure.

Since the observed change from baseline at Week 12 among the non-imputed data will be reported with the MMRM analyses described below, only the LS means, standard errors, 95% CIs, and differences between treatment groups reported with LS means, standard errors, and 95% CIs from the ANCOVA on the imputed data will be reported. The analysis will be completed for both the ITT and PP Populations.

Additionally, the 5-D Itch Scale and the Skindex-10 Scale scores will be analyzed using a mixed effects model with repeated measures (MMRM). The model will contain treatment, week, and treatment-by-week interaction as fixed effects, and baseline score and the randomization stratification variables as covariates. The baseline 5-D total score and the Skindex-10 total score will be defined as the value collected on Day 1, prior to randomization. Repeated measures will include values assigned at the end of Weeks 4, 8, 10, and 12 (end of treatment); see Section [3.1](#) for visit windowing.

It is important to note that, in HD subjects, the study drug administered during the last dialysis of a particular week is not cleared until the first dialysis of the next week. Therefore, measurements that would reflect treatment effect at the end of a specific week (e.g., Week 4) and labelled “end of Week xx” will actually be collected during the first day of the next week (e.g., Week 5).

An unstructured covariance matrix will be used to model the within-subject errors. Should the model fail to converge, a compound symmetric covariance matrix will be used instead. The Kenward-Roger approximation will be used to estimate the denominator degrees of freedom. Missing scores will not be imputed. Assuming that the data are

MAR, the estimates of the treatment differences calculated from the MMRM described above are unbiased.

Standard descriptive statistics will be reported for each time point on the values and changes from baseline along with the least squares (LS) means, standard errors, 95% CIs and differences between treatment groups reported with LS means, standard errors, and 95% CIs.

Worst Itching Intensity ≥ 4 -Point Improvement

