8.2.5.2 Itch-related Quality-of-Life Measures

In addition to the Week 12 results and treatment comparisons, all time points for the 5-D Itch Scale and Skindex-10 will be reported as described in Section [8.2.4.3](#), with the exception of the ANCOVA analysis, and utilized as further efficacy endpoints.

Additionally, the ANCOVA and MMRM analyses described in Section [8.2.4.3](#) for the Skindex-10 will be repeated for all 3 of the Skindex-10 subdomains and the 5 Itch 5-D domains.

The proportion of subjects who have an improvement from baseline in Skindex-10 score of at least 15 points by week will be analyzed and reported along with a logistic regression model-based estimates of the proportions of responders, odds ratio, 95% CIs, and p-value. No imputation of data will be implemented.

The proportion of subjects who have an improvement from baseline in the 5D Itch Scale total score of at least 5 points by week will be analyzed and reported along with a logistic regression model-based estimates of the proportions of responders, odds ratio, 95% CIs, and p-value. No imputation of data will be implemented.

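### The SAP's printed formula for the 5-D Itch total enters duration twice and omits direction, contradicting the five-domain sum stated just above it

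*SAP*

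**What the plan says.** SAP 8.2.4.1 names five dimensions: degree, duration, direction, disability and distribution. Duration, degree and direction are single items scored 1 to 5. Disability is the highest of its four items, and distribution is a binned count of body sites, also scored 1 to 5. The rule in words is "The scores of each of the 5 domains are achieved separately and then summed together to obtain a total 5-D score", with a stated range of 5 to 25.

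The formula that follows begins "Total 5-D Itch score = duration score (single item) + degree score (single item) + duration score (single item"). Its two remaining terms are the highest disability item and the binned body-site score. Direction does not appear in it.

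The total is used in several places:

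- **Gated test (SAP 8.1.3).** The difference between arms "with respect to the 5-D Itch total score will be tested first using the ANCOVA approach". Skindex-10 is tested only if this succeeds, and the ≥4-point NRS endpoint only after Skindex-10.
- **Imputed analysis (SAP 8.2.4.3).** Domains are imputed separately, and then "For each questionnaire, the total score at each visit will be computed from the domain scores for each imputed dataset". This feeds the ANCOVA in the ITT and per-protocol populations. The supportive MMRM uses the same score.
- **Responder analysis (SAP 8.2.5.2).** The cut is "improvement from baseline in the 5D Itch Scale total score of at least 5 points by week".

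Protocol 6.5.3.3 and Appendix 4 include direction but give no rule for the total. SAP section 12, which lists changes from the protocol, records no change to 5-D scoring.

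**The concern.** SAP 8.2.4.1 gives two rules for one derived variable, and they cannot both hold. Neither disability nor distribution supplies the missing direction term.

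A programmer or validator is likely to copy the formula line. The repeated term is a valid variable, so the code would run without an error. Two programmers who each followed the line would agree with each other, so double programming could miss it.

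Coded literally, the score loses the item that asks "Over the past 2 weeks has your itching gotten better or worse compared to the previous month" and gives double weight to hours of itching per day. A further effect concerns missing data. SAP 8.2.4.1 sets the total to missing when a component is missing. Under the literal formula direction is not a component, so a missing direction item would no longer make the total missing.

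**Working it through.** **Inputs.** Five domain scores, each 1 to 5; the sum in words; the printed formula; the stated range of 5 to 25. All are from SAP 8.2.4.1.

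**The two rules**

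- Five-domain sum: S = duration + degree + direction + disability + distribution
- Printed formula: P = 2 × duration + degree + disability + distribution

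**Stated range.** S runs from 5 × 1 = 5 to 5 × 5 = 25, which reproduces the SAP's figure. P runs from 2 + 1 + 1 + 1 = 5 to 10 + 5 + 5 + 5 = 25. The ranges are identical.

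**Error at one visit.** P − S = duration − direction, which runs from 1 − 5 = −4 to 5 − 1 = +4. It is zero only when the two items are equal: 5 × 5³ = 625 of the 5⁵ = 3,125 possible score patterns. This counts patterns and says nothing about how often patients have them.

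**Error in change from baseline.** This equals the change in duration minus the change in direction. Each change runs from −4 to +4, so the error runs from −8 to +8. It is zero when the two changes are equal. A change of k can arise in 5 − |k| ways, so the zero cases number 1 + 4 + 9 + 16 + 25 + 16 + 9 + 4 + 1 = 85 of the 5⁴ = 625 pairings of baseline and Week 12 values. Again this is a count of patterns only.

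**Effect at the 5-point responder cut.** Two hypothetical patients, scores in the order duration, degree, direction, disability, distribution:

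| Patient | Baseline | Week 12 | S (improvement) | P (improvement) |
|---|---|---|---|---|
| A | 3, 3, 4, 4, 3 | 2, 2, 2, 3, 3 | 17 → 12 (5, responder) | 16 → 12 (4, non-responder) |
| B | 4, 3, 4, 4, 3 | 2, 2, 4, 3, 3 | 18 → 14 (4, non-responder) | 18 → 12 (6, responder) |

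The two patients are misclassified in opposite directions, so the error has no fixed sign.

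**What cannot be computed.** The effect on the treatment difference, its standard error, the p-value or power would need the joint distribution of the duration and direction items by arm. The documents do not give it.

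**The case against.** The strongest reply is that this is a misprint the SAP already resolves. The sentence above the formula is a complete scoring rule. SAP 8.2.4.3 imputes every domain and builds the total from the domain scores, and SAP 8.2.5.2 analyses all five domains. A programmer following those sections has direction available and would have to contradict the stated sum to leave it out. The SAP also mentions a scoring manual, so the printed line may not be the programmer's only source. The ±8 error in change needs the two items to move four points in opposite directions. Patients A and B were constructed to sit at the cut, and the responder analysis they illustrate lies outside the multiplicity sequence.

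Most of this stands. The line is very probably a slip, nothing shows that it was coded literally, and the extremes are corner cases. The clause in SAP section 1 that "those found in this SAP will assume primacy" does not help either way: it settles differences between SAP and protocol, whereas this conflict lies within the SAP. The protocol's list of five dimensions supports the five-domain reading, although the protocol states no formula.

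What the reply does not remove is that a derivation rule for the first gated secondary endpoint is wrong as written, in the form most likely to be copied into a specification, with an error that would pass a range check.

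**Conclusion.** The concern holds. The printed formula contradicts the SAP's own definition of the 5-D total, and no recorded change explains it. It should be fixed before database lock.

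The consequence is conditional. If the line is coded literally, visit totals are wrong by up to 4 points and changes from baseline by up to 8, in either direction. The wrong total would enter the gated ANCOVA in both populations, the supportive MMRM and the ≥5-point responder analysis. If the five-domain sum is coded, results do not change.

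The primary endpoint, alpha and sample size are not involved. Both arms would be scored alike, so type I error for the 5-D test would not be inflated; what would change is the quantity being tested. The sizes above rest only on the 1-to-5 scoring of each domain. No correlations, variances or treatment effects were assumed.

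**What to change.** In SAP 8.2.4.1, change the second duration term in the formula to direction.

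Before lock, add one programmed check: for every record with a non-missing total, including each imputed dataset, the total minus the sum of the five domain scores equals zero. Allow a rounding tolerance for imputed values, which may not be whole numbers. Check separately that the total is missing when the direction item is missing in the unimputed data, and that the ≥5-point flag is derived from the checked total.

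The cost is one word in the SAP and a short check on domain scores that are already derived. It has no methodological downside.

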8.2.4.2 Skindex-10 Scale

Developed specifically for uremic pruritus, the Skindex-10 Scale (see protocol Appendix 3) is an instrument for measurement of quality of life. Subjects are asked the question “During the past week, how often have you been bothered by” and respond by filling in 1 of 7 circles numbered from 0 (labeled with the anchor phrase “never bothered”) to 6 (labeled as “always bothered”) for each of the 10 questions.

The total score is the sum of the numeric value of each answered question.

Additionally, the total score is subdivided into 3 domain scores, which are sums of the scores of the following questions: disease domain (questions 1 to 3), mood/emotional distress domain (questions 4 to 6), and social functioning domain (questions 7 to 10).

The scoring manual does not give specific direction regarding scoring when some questions are missing; therefore, the three domains and the total score will be set to missing when any of their individual components are missing. Missing data will be handled implicitly in the MMRM model or explicitly via multiple imputation (see below).

8.2.4.3 Key Secondary Analyses

5-D Itch Scale and the Skindex-10 Scale

The 5-D Itch Scale and the Skindex-10 Scale scores will be analyzed only at Week 12 using an analysis of covariance (ANCOVA). The model will contain treatment as fixed effects, with baseline score and the randomization stratification variables as covariates. The baseline 5-D total score and the Skindex-10 total score will be defined as the value collected on Day 1, prior to randomization. This is a change from the final protocol dated 21DEC2017 and is being implemented to address the FDA advice received on 10JAN2019 stating that “*the analysis [of continuous efficacy endpoints] should be based on only data from one timepoint (e.g. Week 12); however, modeling approaches using all timepoints may be used as supportive analyses.*”

Additionally, subjects who discontinue treatment but continue on study and have 5-D and Skindex-10 scores recorded will have these scores censored following discontinuation of treatment; missing data rules will apply to these censored values as though they had missing values/ dropped out from the study entirely.

For each domain in each questionnaire, missing values at Week 12 will be imputed using an MI approach, assuming that subjects who discontinue double-blind treatment early would have similar 5-D Itch and Skindex-10 scores as other subjects in their respective treatment arm that have complete data. All available visits will be included in the MI to

better inform the Week 12 imputed results. The MI approach will proceed as follows, using all ITT subjects (that is, it will not be split into IA subjects and post- IA subjects):

- Intermittent missing scores will first be imputed using the Markov Chain Monte Carlo (MCMC) method implemented with the SAS MI procedure, which is appropriate for non-monotonic missing data.
- The monotone missing values will then be multiply imputed with the SAS MI procedure using the monotone regression method.
- For each stage, MI will be performed within treatment group with covariates for baseline score, both randomization stratification factors, and all non-missing visit scores for each domain of the questionnaire. Should convergence issues occur due to small cell size for the categorical covariates at either stage, they will be removed from the model.
- Twenty imputations will be performed for each domain.
- For each questionnaire, the total score at each visit will be computed from the domain scores for each imputed dataset.
- The ANCOVA analysis described above will be implemented for each imputed dataset.
- Results of the ANCOVA on the multiply imputed data sets will be summarized by the SAS MIANALYZE procedure.

Since the observed change from baseline at Week 12 among the non-imputed data will be reported with the MMRM analyses described below, only the LS means, standard errors, 95% CIs, and differences between treatment groups reported with LS means, standard errors, and 95% CIs from the ANCOVA on the imputed data will be reported. The analysis will be completed for both the ITT and PP Populations.

Additionally, the 5-D Itch Scale and the Skindex-10 Scale scores will be analyzed using a mixed effects model with repeated measures (MMRM). The model will contain treatment, week, and treatment-by-week interaction as fixed effects, and baseline score and the randomization stratification variables as covariates. The baseline 5-D total score and the Skindex-10 total score will be defined as the value collected on Day 1, prior to randomization. Repeated measures will include values assigned at the end of Weeks 4, 8, 10, and 12 (end of treatment); see Section [3.1](#) for visit windowing.

It is important to note that, in HD subjects, the study drug administered during the last dialysis of a particular week is not cleared until the first dialysis of the next week. Therefore, measurements that would reflect treatment effect at the end of a specific week (e.g., Week 4) and labelled “end of Week xx” will actually be collected during the first day of the next week (e.g., Week 5).

An unstructured covariance matrix will be used to model the within-subject errors. Should the model fail to converge, a compound symmetric covariance matrix will be used instead. The Kenward-Roger approximation will be used to estimate the denominator degrees of freedom. Missing scores will not be imputed. Assuming that the data are

MAR, the estimates of the treatment differences calculated from the MMRM described above are unbiased.

Standard descriptive statistics will be reported for each time point on the values and changes from baseline along with the least squares (LS) means, standard errors, 95% CIs and differences between treatment groups reported with LS means, standard errors, and 95% CIs.

Worst Itching Intensity ≥ 4 -Point Improvement

The proportion of subjects achieving ≥ 4 -point improvement from baseline with respect to the weekly mean of the daily 24-hour Worst Itching Intensity NRS at Week 12 of the Double-blind Treatment Period will be analyzed following a methodology identical to the one employed for the primary analysis of the primary endpoint (see section 8.2.2). The same dataset will be utilized; separate flags for various cut points of improvement will be utilized to facilitate these analyses. The analysis will be completed for both the ITT and PP Populations.

